3.2 ENDPOINTS

3.2.1 Immunogenicity Endpoints

The primary immunogenicity endpoint is the proportion of participants achieving a four times or greater increase in NAC by Week 4 compared with Week 0. A positive response will be defined as achieving this level of increase in at least 50% of the participants for botulinum toxin type A and type B.

The secondary immunogenicity endpoints are as follows:

- The proportion of participants achieving a two times increase in the area under the plasma concentration-time curve between Week 0 and Week 12 in NAC in comparison to a straight-line extension of the Week 0 NAC to Week 12. A positive response will be defined as achieving this level of increase in at least 50% of the participants for botulinum toxin type A and type B.

- The proportion of participants achieving a three times or greater increase in NAC by Week 4 compared with Week 0. A positive response will be defined as achieving this level of increase in at least 50% of the participants for botulinum toxin type A and type B.

3.2.2 Safety Endpoints

Safety endpoints will be as follows:

- Frequency of injection site reactions and systemic reactions that are characterized as severe during the 0-7 day diary collection period
- Frequency of injection site reactions and systemic reactions that are characterized as SAEs
- Participant incidence of treatment-related SAEs
- Participant incidence of serious NOCIs
- Clinically significant changes from baseline health resulting in SAEs
- Clinically significant changes in hematology between screening and Week 4 resulting in severe or serious adverse events

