Diary review			X					
Serious adverse event collection ^r		X	X	X	X		X	X
Concomitant medication information	X ^t		X ^s	X ^s	X ^s		X ^s	X ^s
Phone call			X	X	X			X

HBV = hepatitis B virus; HCV = hepatitis C virus; HIV = human immunodeficiency virus; NAC = neutralizing antibody concentration; rBV A/B = recombinant botulinum vaccine A/B.

a. Week 1, Week 4, and Week 10 Follow-up Calls must occur with ± 3 days of the scheduled time.

b. Final Study Visit will be an on-site visit at Week 4 for participants who opt not to participate or who have been determined to be ineligible for donation for the entire study. All final assessments occurring at Week 12 will occur at Week 4 for these participants.

c. Extension of plasmapheresis for up to 14 weeks is optional

- d. Final on-site Study Visit must occur within \pm 7 days of the scheduled time.
- e. Final follow-up call for safety must occur within \pm 1 week of the scheduled time.
- f. Plasmapheresis-specific informed consent formed will be signed at the source plasma center.
- g. Physical examination will be performed as part of source plasma donor screening at the plasma collection center
- h. Female participants of childbearing potential must have a negative pregnancy test within 24 hours prior to vaccination.
- i. Participants will have vital signs taken twice at Visit 1: prior to injection, and 30 minutes (\pm 5 minutes) after receiving the injection.
- j. HIV, HBV, and HCV tests will be performed on each donated source plasma unit
- k. Results from screening tests must be available before Vaccination Visit
- l. Study participants will go to central lab or plasma center for this draw (not an on-site visit).
- m. Baseline NAC sample must be collected before rBV A/B injection and before plasmapheresis
- n. Participants not donating plasma must go to site for NAC collection within \pm 3 days of the scheduled time.
- o. May occur up to twice a week for up to 14 weeks (if hemoglobin and total protein remain within acceptable range) following vaccination with rBV A/B.
- p. At this visit, participants will be monitored for at least 30 minutes after injection for a possible reaction.
- q. In the diaries, participants record adverse events in order to determine SAE, oral temperature and injection site information.
- r. Only serious adverse events and new onset chronic illnesses are to be queried for and collected

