5.2.2.3 Telephone Call (Week 1)

Study personnel will call participants at Week 1 (\pm 3 days) to review the Reaction Recording Sheet – Participant Home Diary injection site and systemic reactions, as well as any potential SAEs occurring over the past week and any NOCIs and concomitant medications. Study personnel should inquire about participants overall well-being and any concomitant medications. Participants should use the provided Adverse Event Recording Sheet for Identification of Possible Serious Adverse Events form ([Appendix E](#)) between phone calls to assist during the inquiry. The information recorded by the delegated site personnel during the phone call will serve as the source documentation.

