5.2.2.4 Week 4 Visit and Laboratory Draws

Participants not participating in plasma donation must return to the site at Week 4 (\pm 3 days) for their final study visit. During this visit, the following activities will occur:

- Injection site inspection

- Review of serious adverse events
- Review of any new onset chronic illnesses
- Collection of concomitant medication information, if any
- Collection of 20 mL of blood to determine NAC
- Urine pregnancy test for female participants of childbearing potential
- Repeat of hematology conducted at screening (Section [5.2.1](#))
- Completion of final on-site study record

Total blood volume collected at this visit will be 25 mL (20 mL for NAC and 5 mL for hematology). Total urine volume collected will be approximately 10 mL for the urine pregnancy test.

All participants continuing in the study will go to a central lab or plasma center (not on site) for hematology.

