5.2.3 Final Study Follow-up (Day 182, Week 26)

Within 1 week of Week 26, site personnel will contact the participant by phone to assess the participant's general health status. Interim occurrence of any SAEs or serious NOCIs will be queried for and recorded. Any concomitant medications used to treat SAEs or serious NOCIs will be recorded and entered in the eCRF.

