Within 1 week of Week 26, site personnel will contact all participants by phone to assess their general health status. Interim occurrence of any SAEs or NOCIs will be queried for and recorded. Any concomitant medications used to treat SAEs or NOCIs will be recorded.

NAC sample collections are required for all participants at Week 0 and Week 4. For plasma-donating participants, NAC sample collection is required with each donated unit.

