8.1 SERIOUS ADVERSE EVENTS AND ADVERSE EVENTS OF INTEREST

Only SAEs and AEs of special interest will be evaluated for this study. AEs of special interest will include a) severe localized injection site reactions and severe systemic reactions that occur from Day 0 to Day 7 and b) severe clinically significant changes in hematology between screening and Week 4. SAEs will be recorded from administration of the investigational product at the vaccination visit through the follow-up phone call at Week 26. AE data will be coded using MedDRA v22.0.

Severe localized injection site reactions and severe systemic reactions that occur from Day 0 to Day 7 will be summarized by category (localized or systemic) and maximum severity. An overall summary with point estimates of incidence and 95% confidence intervals will be provided for severe localized injection site reactions and severe systemic reactions, along with average durations for each. Clinically significant changes in hematology between screening and Week 4 and related SAEs will also be summarized by maximum severity.

A summary of all SAEs by system organ class and preferred term will be produced. A similar summary will be produced for SAEs that are categorized as NOCIs (serious NOCIs). Summaries by maximum severity and strongest relationship to vaccine will be produced for all SAEs. SAEs, serious NOCIs, severe localized injection site reactions and severe systemic reactions, clinically significant changes in hematology between screening and Week 4, AEs resulting in death, and AEs leading to discontinuation from the study will be provided in appendix listings of the clinical study report.

When calculating the incidence of AEs, each AE will be counted only once for a given participant within a MedDRA category (e.g., overall, system organ class, or preferred term). When AEs are summarized within levels of another AE assessment (e.g., causality or severity), AEs will be counted once per participant at the worst level of the assessment (e.g., strongest relationship to study drug or greatest severity).

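### The documents disagree on whether all new onset chronic illnesses or only serious ones are queried and recorded, and non-serious ones enter no endpoint or planned summary

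*SAP*

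**What the plan says.** Endpoint and analysis: Protocol 3.3.2 and SAP 3.2.2 name the same endpoint, "Participant incidence of serious NOCIs". After describing the SAE table, SAP 8.1 adds: "A similar summary will be produced for SAEs that are categorized as NOCIs (serious NOCIs". The same section sets the overall scope: "Only SAEs and AEs of special interest will be evaluated for this study". The events of special interest are severe reactions in the first week and severe hematology changes up to Week 4.

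Collection: the Week 1 call (Protocol 5.2.2.3) covers "any potential SAEs occurring over the past week and any NOCIs and concomitant medications". The Week 4 visit for non-donors (Protocol 5.2.2.4) includes "Review of any new onset chronic illnesses". For Week 26, SAP 1.6 says "Interim occurrence of any SAEs or NOCIs will be queried for and recorded", whereas Protocol 5.2.3 says "Interim occurrence of any SAEs or serious NOCIs will be queried for and recorded". Footnote r to the schedule of events, identical in both documents, says "Only serious adverse events and new onset chronic illnesses are to be queried for and collected".

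The abbreviation NOCI is spelled out, but the text provided does not define which illnesses count.

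**The concern.** Safety at 6 months is a stated objective in both documents. Beyond the reaction week, NOCIs are the only non-laboratory category that the plan names alongside SAEs. If only serious NOCIs are counted, and each of them is already an SAE, the NOCI endpoint adds a label but no events.

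A new chronic diagnosis managed in outpatient care need not meet the seriousness criteria in Protocol 6.1. Such a diagnosis can be asked for, reported by the participant, written in the source record and never reach the database. Whether that happens depends on which section a site follows. The synopsis gives two sites, so the 6-month data could differ by site for reasons unrelated to the vaccine.

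**Working it through.** The documents state no NOCI rate, power or precision, so there is no figure to reproduce. The check is a comparison of wording.

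**Step 1: what each contact asks and records.**

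| Contact | NOCIs generally | Serious NOCIs only |
|---|---|---|
| Week 1 call | Protocol 5.2.2.3; SAP 1.6 | none |
| Week 4 visit, non-donors | Protocol 5.2.2.4 | none |
| Weeks 4 and 10 calls, donors | Protocol 5.2.2.5, for the question | Protocol 5.2.2.5, for the eCRF entry |
| Week 12 visit | Protocol 5.1; SAP 1.6 | Protocol 5.2.2.6 |
| Week 26 call | SAP 1.6 | Protocol 5.2.3; synopsis |
| Medication used to treat | SAP 1.6, at Week 26 | Protocol 4.5 and 5.2.3; footnote s in both documents |
| Schedule, all contacts | Footnote r, on one reading | Footnote r, on the other reading |

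The contradiction is direct at Week 12 (within the Protocol) and at Week 26 (between Protocol and SAP). At the Week 4 and Week 10 calls the question is wider than the record.

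**Step 2: follow a non-serious NOCI to the report.** It is not an SAE, so it is outside the SAE table and outside the serious NOCI summary drawn from it. Unless it happens to be one of the two kinds of event of special interest, it is outside that group too. The one planned output that could show it is the SAP 8.1 listing of adverse events leading to discontinuation.

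**Step 3: the time affected.** Under the Protocol's visit-level sections, the last contact that asks about any NOCI is Week 4 for non-donors and Week 10 for donors. The stretch in which only serious NOCIs are sought is then 26 − 4 = 22 weeks for non-donors and 26 − 10 = 16 weeks for donors. Under SAP 1.6, the Week 26 call asks about all NOCIs and the stretch disappears. What a 6-month NOCI figure covers therefore depends on which text was used.

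**Step 4: scale, for illustration only.** Let p be the proportion of participants with any NOCI by Week 26 and s the share of those that are serious. Neither is in the documents; I assume p from 2% to 10% and s from 5% to 50%. With n = 50, the chance of at least one event is 1 − (1 − p)^50 for any NOCI and 1 − (1 − ps)^50 for a serious one.

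| p | At least one NOCI | At least one serious NOCI, s = 5% to 50% |
|---|---|---|
| 2% | 63.6% | 4.9% to 39.5% |
| 5% | 92.3% | 11.8% to 71.8% |
| 10% | 99.5% | 22.2% to 92.3% |

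If no serious NOCI were seen in 50 participants, the exact two-sided 95% upper limit would be 1 − 0.025^(1/50) = 7.1%. That limit would apply to serious NOCIs only.

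**The case against.** The restriction to serious NOCIs looks deliberate. It appears in the synopsis, Protocol 3.3.2, 4.5, 5.2.2.5, 5.2.2.6 and 5.2.3, and SAP 3.2.2 and 8.1. Footnote r annotates the row for serious adverse event collection, its adjective can govern both nouns, and footnote s supports the narrow reading. An endpoint that is a subset of SAEs is not in itself a defect: treatment-related SAEs are another. SAP 8.1 is open about the overlap. The Protocol also rests on earlier experience, including 372 participants at the same dose level.

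Nor does a non-serious NOCI vanish entirely. Protocol 6.1 sends all complaints to the source documents, and its criterion for other important medical events lets an investigator classify some outpatient diagnoses as serious. Related neuromuscular events count toward a stopping rule in Protocol 4.4.2 without any seriousness requirement.

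Much of this stands. In particular, a reader might infer that participants are asked about all NOCIs at every contact to 6 months, and that the 6-month follow-up therefore cannot show what it asks about. The documents do not support that. Protocol 5.2.2.6, 5.2.3 and the synopsis limit the Week 12 and Week 26 questions themselves to serious NOCIs, which matches the endpoint. A 6-month mismatch arises only under SAP 1.6 and the wide reading of footnote r. A reader might also infer that the report will state zero NOCIs; the planned outputs are labelled as serious NOCIs.

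The objection does not remove the conflict at Weeks 12 and 26, or the narrowing between question and eCRF at Weeks 4 and 10. Source records are not the analysis database, and the important-medical-event route rests on judgment that may differ between sites.

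**Conclusion.** The point holds as an inconsistency in collection with a consequence for reporting. The documents disagree on which NOCIs are sought and recorded. The sole NOCI endpoint lies within the SAEs. Non-serious NOCIs that participants report have no planned summary, and no listing unless they cause discontinuation. These conclusions rest on the text alone.

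The size in events cannot be fixed from the documents. Step 4 shows only that, over the assumed ranges, the chance of seeing an event is lower for the serious endpoint than for all NOCIs, by an amount that depends strongly on the assumed serious share. I give no percentage of information lost, because it would simply be one minus that assumed share. With at most 50 participants, one arm and no comparator, the data would be descriptive either way. The change is worth making because it is cheap and serves a stated objective. It does not bear on the immunogenicity conclusions.

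**What to change.** 1. Define NOCI once in the Protocol and refer to that definition in the SAP. Without it, wider collection would itself vary by site.
2. Reconcile the Protocol synopsis, 4.5, 5.1, 5.2.2.3 to 5.2.2.6 and 5.2.3, SAP 1.6, and footnotes r and s in both documents. Each should say that every NOCI reported at the existing contacts through Week 26 is recorded in the eCRF with onset date, seriousness and causality. Changing only some of these would create new contradictions.
3. In SAP 8.1, extend the scope sentence to NOCIs and add a listing and participant incidence of all NOCIs. Keep serious NOCIs as the stated subset, and say in Protocol 3.3.2 and SAP 3.2.2 that these are also SAEs.

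Cost: no new visits or calls. The Week 12 and Week 26 questions change wording, the eCRF takes some additional entries, and a few non-serious diagnoses must be coded and assessed.

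If the sponsor prefers the narrow scope, the minimum is to define NOCI and state throughout both documents that only serious NOCIs are queried and recorded, and that they are a subset of SAEs. That removes the contradiction, but non-serious chronic illness would then remain outside the 6-month safety information.

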3.2.3 Exploratory Endpoints

The exploratory endpoint will be the volume of source plasma containing neutralizing antibodies against botulinum toxin type A and type B collected by plasmapheresis for use in BabyBIG manufacture.

3.3 METHODS FOR HANDLING DROPOUTS AND MISSING DATA

No imputation will be made for missing data, with the exception that partially missing dates will be imputed to the least favorable date. For example, AEs with partially missing dates that occur in the same month as dose administration will be considered treatment emergent.

Participant dropouts will not be replaced.

3.4 VISIT WINDOWS

Immunogenicity values (NAC values) will be assigned to weeks/visits according to the visit windows listed in Section 7.3. For displays using the per protocol population, immunogenicity assessment values which are collected outside the visit windows for the relevant time points will be excluded from per protocol analyses.

Safety values will be evaluated and displayed as belonging to the intended visit, regardless of the actual study day on which they were collected.

3.5 DISPLAY SPECIFICATIONS

Displays will be produced by using the Courier New 8-point font. Headers will also be in Courier New 8-point font.

All displays are intended to be printed as landscape on 8.5-in × 11-in paper. The top and bottom margins will be 0.50 in, and the left and right margins will be 0.75 in.

Relative to the number of digits after the decimal in the original data, summary statistics will have the following number of digits after the decimal: mean, median, and percentiles - one more digit; standard deviation and standard error - two more digits; minimum, maximum, and range - same number of digits. Summary statistics will not exceed four digits after the decimal. Some laboratory parameters or other data may require judicious deviation from this rule.

Percentages will be displayed with one digit after the decimal.

3.6 DATA AND SAFETY MONITORING BOARD

A data and safety monitoring board (DSMB) meeting will take place quarterly throughout the study and as needed. Details regarding the displays to be provided for the DSMB meetings will be determined separately from this statistical analysis plan.

4.0 ENROLLMENT AND DISPOSITION

Participant enrollment, inclusion in analysis populations, number of participants discontinuing before study completion, and reasons for premature discontinuation will be summarized with frequencies and, where appropriate, percentages of enrolled participants. Data will also be provided in an appendix listing of the clinical study report.

5.0 EVALUATION OF BASELINE VALUES**5.1 DEMOGRAPHICS AND BASELINE CHARACTERISTICS**

Demographic and baseline characteristic data will be collected prior to vaccination. All demographic and baseline characteristic data will be summarized and listed.

5.2 MEDICAL HISTORY

Medical history is collected during Screening (Days -7 to -1). Medical history data will be listed.

6.0 EVALUATION OF TREATMENT EXPOSURE AND COMPLIANCE

A single dose of the rBV A/B vaccine will be administered to each participant at the Vaccination Visit (Day 0). The vaccine formulation is 40 µg total antigen (20 µg Antigen A and 20 µg Antigen B) with 100 mM sodium chloride, 15 mM sodium phosphate, and 50 mM sodium acetate with Alhydrogel™ (0.2% weight per volume) balanced to a pH of 5.5 for a total dose volume of 0.5 mL. Vaccine administration and exposure data, including whether or not each participant received the injection, will be provided in an appendix listing of the clinical study report.

7.0 EVALUATION OF IMMUNOGENICITY PARAMETERS

The immunogenicity population will be used for all immunogenicity endpoints. The PP population will be used in the case that any sensitivity analyses are deemed necessary.

All immunogenicity endpoints will be performed for both botulinum toxin type A and type B.

7.1 ANALYSIS OF PRIMARY IMMUNOGENICITY ENDPOINT

The primary immunogenicity endpoint is the proportion of participants achieving a four times or greater increase in NAC by Week 4 compared to Week 0. The cut-off value for determining whether the increase is achieved for each subject will be calculated as $[(\text{Week 0 value}) \times 4] + (\text{Week 0 value})$. A positive response will be defined as achieving this level of increase in NAC in at least 50% of participants. The proportion of participants who achieve this level of increase in NAC will be provided along with a 95% confidence interval. Graphs may be used to show corresponding participant-level data.

This primary analysis will be performed for both botulinum toxin type A and type B. In the event that the primary endpoint is not met for neutralizing antibodies against botulinum toxin type A or type B, the Sponsor-Investigator will determine if the plasma collected during the study contains sufficient antibody titers for meeting specifications for BabyBIG production. If so, the trial will still be considered successful.

Details regarding the collection schedule for blood samples for NAC can be found in Section 7.3.

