3.3 ENDPOINTS

3.3.1 Immunogenicity

The primary immunogenicity endpoint is the proportion of participants achieving a four times or greater increase in NAC by Week 4 compared with Week 0. A positive response will be defined as achieving this level of increase in at least 50% of the participants for botulinum toxin type A and type B.

The secondary immunogenicity endpoints are as follows:

- The proportion of participants achieving a two times increase in the area under the plasma concentration-time curve between Week 0 and Week 12 in NAC in comparison to a straight-line extension of the Week 0 NAC to Week 12. A

positive response will be defined as achieving this level of increase in at least 50% of the participants for botulinum toxin type A and type B.

- The proportion of participants achieving a three times or greater increase in NAC by Week 4 compared with Week 0. A positive response will be defined as achieving this level of increase in at least 50% of the participants for botulinum toxin type A and type B.

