6.10 DATA AND SAFETY MONITORING BOARD

The DSMB will meet quarterly throughout the study and as needed as described in Section 4.4. The specific information that will be reviewed to make its recommendation will be safety data and neutralizing antibody concentrations.

In addition, the DSMB will convene at any time during the study if a stopping rule is met (see Section 4.4.2)

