8.2.4 Immunogenicity Analysis

The immunogenicity population will be used for all immunogenicity endpoints. The per protocol population will be used in the case that any sensitivity analyses are deemed necessary.

The immunogenicity parameters are concentrations of neutralizing antibodies against botulinum toxin type A and toxin type B. These parameters will be analyzed by using NAC data from a validated mouse neutralization assay.

For the primary endpoint, a positive response will be defined as achieving a greater than or equal to four times increase (point estimate) above baseline in NAC by Week 4 compared with Week 0 in at least 50% of the participants in the immunogenicity population for botulinum toxin type A and type B, respectively.

A point estimate and two-sided 95% confidence interval for the proportion of participants who achieve this endpoint will be provided.

For the first secondary immunogenicity endpoint, a positive response will be defined as achieving a two times increase above baseline in the estimated area under the plasma NAC-time curve in the period from Week 0 to Week 12 in comparison to straight-line extension of the Week 0 antibody concentration from Week 0 to Week 12 in least 50% of the participants.

For the second secondary immunogenicity endpoint, a positive response will be defined as is achieving a three times or greater increase in NAC above baseline by Week 4 in at least 50% of the participants for botulinum toxin type A and type B. A point estimate and two-sided 95% confidence interval for the proportion of participants who achieve this endpoint will be provided.

Further details of the analysis, will be provided as needed in a separate statistical analysis plan.

In the event that the primary endpoint is not met for neutralizing antibodies against botulinum toxin type A and type B, the sponsor-investigator will determine if the plasma collected during the study contains sufficient antibody titers for meeting specifications for BabyBIG production. If the immune responses meet specifications to permit the production of BabyBIG, then the trial will still be considered successful. Also, a second booster dose of rBV A/B vaccine may be considered; however, this will require operational modifications (e.g., a protocol amendment and updated consent form).

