7.2 ANALYSIS OF SECONDARY IMMUNOGENICITY ENDPOINTS

All secondary immunogenicity endpoints will use the immunogenicity population.

The first secondary immunogenicity endpoint is the proportion of participants achieving a two times increase in the estimated area under the plasma concentration-time curve in the period between Week 0 to Week 12 in comparison to straight-line extension of the Week 0 NAC to Week 12. The cut-off value for determining whether

the increase is achieved for each subject will be calculated as (Week 0 value) x (total number of days from Week 0 to Week 12 collection) x 2. A positive response will be defined as achieving this level of increase in at least 50% of the participants. If a participant does not have NAC collections through Week 12, the date of the last NAC collection will be used in place of the Week 12 date for both the concentration-time curve and the straight-line extension. In the cases where there are multiple NAC values on the same date for a particular subject, the mean of those values will be used in calculating the estimated area under the plasma concentration-time curve.

The second secondary immunogenicity endpoint is the proportion of participants achieving a three times or greater increase in NAC above baseline by Week 4 compared to Week 0. The cut-off value for determining whether the increase is achieved for each subject will be calculated as [(Week 0 value) x 3] + (Week 0 value). A positive response will be defined as achieving this level of increase in at least 50% of the participants.

Proportions will be provided for both secondary endpoints along with 95% confidence intervals.

Further details regarding the collection schedule for blood samples for NAC can be found in Section 7.3.

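### SAP 7.1 and 7.2 code the Week 4 increases additively (5× and 4× Week 0) but the AUC increase as a ratio (2×), so under any single convention at least one pass/fail cut-off is wrong.

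*SAP*

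**What the plan says.** Protocol 3.3.1 gives the primary endpoint as "the proportion of participants achieving a four times or greater increase in NAC by Week 4 compared with Week 0". Protocol 8.2.4 restates it as "achieving a greater than or equal to four times increase (point estimate) above baseline in NAC by Week 4 compared with Week 0", and describes the first secondary endpoint as "achieving a two times increase above baseline in the estimated area under the plasma NAC-time curve", compared with the Week 0 value carried forward as a straight line to Week 12. The second secondary is a three times or greater increase above baseline by Week 4. Each endpoint is positive if at least 50% of participants reach it.

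The protocol gives no formula for any of the three and defers: "Further details of the analysis, will be provided as needed in a separate statistical analysis plan".

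The SAP supplies the formulas:

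- Primary (SAP 7.1): "calculated as $[(\text{Week 0 value}) \times 4] + (\text{Week 0 value").
- Second secondary (SAP 7.2): "Week 0 value) x 3] + (Week 0 value").
- AUC secondary (SAP 7.2): "Week 0 value) x (total number of days from Week 0 to Week 12 collection) x 2".

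**The concern.** All three endpoints are worded as a number of times increase, and Protocol 8.2.4 describes the primary and AUC endpoints alike, as increases above baseline. The SAP nevertheless adds the baseline back for the two Week 4 endpoints and not for AUC.

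Success rests on a point estimate of at least 50% for each toxin, in at most 50 participants and with no power calculation (Protocol 8.2.6, SAP 1.4). Participants who fall between 4× and 5× at Week 4, or between 2× and 3× on AUC, can therefore decide the result. If a ratio was meant, the primary and second secondary are judged at too high a bar. If an additive increase was meant, the AUC endpoint is judged at too low a bar and could be declared positive wrongly.

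Timing matters too. The study is open-label, and Protocol 6.10 says of the DSMB: "The specific information that will be reviewed to make its recommendation will be safety data and neutralizing antibody concentrations". A convention chosen after NAC data have been seen would be open to the charge that it was chosen to fit.

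**Working it through.** **Cut-offs as coded.** Let b be the Week 0 NAC and D the number of days from Week 0 to the Week 12 collection.

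- Primary: 4b + b = 5b.
- Second secondary: 3b + b = 4b.
- AUC: the straight-line area is b × D and the cut-off is b × D × 2, so the required ratio is 2bD / bD = 2. With b = 1 and D = 84, this is 168 / 84 = 2.

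**Comparison with each single convention.**

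| Endpoint | SAP as coded | Ratio rule | Additive rule |
|---|---|---|---|
| Primary, four times | 5× | 4× | 5× |
| Second secondary, three times | 4× | 3× | 4× |
| AUC, two times | 2× | 2× | 3× |

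Under the ratio rule two of the three cut-offs are out of line; under the additive rule one is. The coded second secondary (4×) is also the ratio reading of the primary, and no Week 4 proportion at 3× is planned.

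One reading would rescue the AUC formula. If the area were incremental (only the part above baseline), requiring 2bD would be additive. SAP 7.2 uses the total area under the concentration-time curve, so that reading is not supported.

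**Effect on the 50% rule.** The documents give no response distribution, so this is an illustration. It assumes a log-normal fold rise with log10 SD s of 0.3 to 0.6, n = 50 (the enrolment cap) and one toxin. If a proportion p4 reaches 4×:

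- mean of log10 fold rise: μ = log10(4) + s × z(p4)
- proportion reaching 5×: p5 = 1 − Φ((log10(5) − μ) / s)
- chance of passing at a bar reached by proportion p: P(X ≥ 25), X ~ Binomial(50, p)

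| p4 (reach 4×) | p5 (reach 5×) | Pass at 4× | Pass at 5× |
|---|---|---|---|
| 0.45 | 0.33–0.39 | 0.28 | 0.01–0.07 |
| 0.50 | 0.37–0.44 | 0.56 | 0.05–0.22 |
| 0.55 | 0.42–0.49 | 0.80 | 0.16–0.48 |
| 0.60 | 0.47–0.54 | 0.94 | 0.40–0.75 |
| 0.70 | 0.58–0.64 | 0.999 | 0.90–0.99 |
| 0.80 | 0.70–0.75 | >0.999 | at least 0.999 |

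The same calculation for AUC replaces 4 and 5 by 2 and 3, with the same SD range assumed for the area ratio:

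| p2 (reach 2×) | p3 (reach 3×) | Pass at 2× | Pass at 3× |
|---|---|---|---|
| 0.55 | 0.32–0.43 | 0.80 | 0.01–0.21 |
| 0.70 | 0.48–0.59 | 0.999 | 0.42–0.93 |
| 0.80 | 0.60–0.71 | >0.999 | 0.94–0.999 |

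**The case against.** The strongest reply is that nothing is left undefined. The protocol hands the detail to the SAP, and the SAP gives an explicit formula for every endpoint. Adding the Week 0 value back is also a literal implementation of an increase above baseline. On that reading both Week 4 cut-offs are right and only one secondary is out of line. The AUC endpoint has its own comparator, the straight-line extension, and SAP 7.2 does not repeat the words above baseline for it, so a separate rule there could be defended.

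The consequences are also limited. If a ratio was meant, the coded primary is stricter than intended, which does not make a false positive more likely. The 4× proportion is still reported with its confidence interval as the second secondary. Under Protocol 8.2.4 and SAP 7.1, a missed primary can still count as a successful trial if the plasma meets BabyBIG specifications. Any other cut-off can be computed from the same data.

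Most of this is fair as mitigation, but it does not remove the inconsistency. Explicit formulas settle what will be programmed, not whether it matches the protocol endpoint. If the additive reading is accepted for Week 4, the AUC cut-off is wrong, because Protocol 8.2.4 does describe that endpoint as an increase above baseline. The BabyBIG route is a separate determination by the sponsor-investigator and does not correct the endpoint. It also stands that the documents do not show the primary bar itself to be wrong.

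**Conclusion.** The concern holds. The multiples 5, 4 and 2 follow directly from the SAP's formulas, no passage reconciles them, and no single convention produces them. At least one stated pass/fail rule is therefore wrong as written. Which one cannot be settled from the documents.

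The size of the effect depends on the response rate. Under the assumptions above, the primary conclusion is sensitive when roughly 45% to 65% of participants reach 4×. At 70% it passes with probability of at least 0.90 at either bar, and at 80% the difference disappears. The AUC conclusion is sensitive over a wider range: even with 70% reaching 2×, the chance of passing falls from 0.999 to between 0.42 and 0.93 if the bar is 3×. These probabilities rest on log-normality, the assumed SD range, full enrolment of 50 and one toxin considered alone. The inconsistency itself rests on none of them.

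This must be fixed, because it concerns the responder definition of the primary endpoint and costs very little to correct.

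**What to change.** Before NAC results are reviewed, choose one convention for all three endpoints and state each threshold as an explicit multiple of Week 0 (or of the straight-line Week 0 area) in Protocol 3.3.1 and 8.2.4 and in SAP 7.1 and 7.2. The choices are:

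- **Ratio:** Week 4 NAC at least 4× and 3× Week 0, and AUC at least 2× the straight-line area. This changes the two Week 4 formulas.
- **Additive:** Week 4 NAC at least 5× and 4× Week 0, and AUC at least 3× the straight-line area. This changes the AUC formula, and the protocol should then state the multiples 5, 4 and 3.

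Under either choice, report the Week 4 proportions at 3×, 4× and 5× with 95% confidence intervals for each toxin, so that readers can see how far the conclusion depends on the bar. If any NAC results have already been seen, record that and report the success rules under both conventions.

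The cost is a small wording change in each document (a protocol amendment if the 5× and 4× bars are kept) and about one line of SAS code per endpoint. No new data are needed.
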